## 5.3 CNS Events (Bleed, Thrombosis or Infarction)

Hold asparaginase. Treat with FFP, factors or anticoagulation as appropriate. Resume at full dose when all symptoms have resolved (and evidence of recanalization in case of thrombosis by CT/MRI). Consider evaluation for inherited predisposition to thrombosis.

## 5.4 Coagulopathy

If symptomatic, omit Day 9 asparaginase (*E.coli* or *Erwinia*) and consider factor replacement (FFP, cryoprecipitate). Do not hold asparaginase (*E.coli* or *Erwinia*) for abnormal laboratory findings without clinical symptoms.

## 5.5 Hepatic Toxicity

### 5.5.1 Transaminases

If the ALT or AST are  $> 10\text{x ULN}$ , attempts should be made to identify the cause. In most cases, the therapy may proceed without modification.

### 5.5.2 Hyperbilirubinemia

If the conjugated/direct bilirubin is  $> 3 \text{ mg/dL}$  and is not a result of the leukemia, modify the doses of daunorubicin, etoposide, and mitoxantrone as follows below. For all cases in which the direct bilirubin is elevated at the point in time that the next cycle is to begin, consider delaying the cycle for 1 week to determine whether the direct bilirubin falls to an acceptable level.

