### 3.2.4 Organ Function Requirements

There are no minimal organ function requirements for enrollment on this study.

**Note:** See [Section 5.0](#) for dose adjustment in case of significant organ dysfunction. Previous cardiac repair with sufficient cardiac function as outlined in [Section 5.0](#) is not an exclusion criteria.

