4.2.2 Required Observations in Induction I

**All baseline studies (a-m below) must be performed prior to starting protocol therapy unless otherwise indicated below.**

- a. Physical exam, CBC with differential & platelets, twice weekly while in the hospital.
- b. Creatinine, BUN, weekly while in the hospital.
- c. Electrolytes (Ca++, Mg++, PO4), weekly while in the hospital.
- d. AST, ALT, bilirubin (unconjugated and conjugated), weekly while in the hospital.
- e. Height, weight.
- f. ECG.
- g. ECHO or MUGA.
- h. Unilateral bone marrow aspirate (BMA); biopsy if unable to obtain a BMA
- i. Bone marrow baseline immunophenotype (Immunophenotyping including CD41 and/or CD61, CD33, CD34, CD14, CD7 and Gly-A is strongly recommended).
- j. CSF cell count and cytospin.
- k. BMA for MRD, submit sample to Hematology (peripheral blood may be used for baseline sample, see [Section 14.1](#)).
- l. Optional bone marrow sample for *GATA1* mutation analysis (see [Section 14.1](#)).
- m. Optional bone marrow sample for banking (see [Section 14.1](#)).

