##### **MitoXANTRONE: IV over 15 to 30 minutes**

Days: 3-6.

All patients: 0.4 mg/kg/day

Administer through the tubing of a rapidly infusing solution of D5W or 0.9% NaCl. Avoid extravasation; the use of a central line is suggested.

Note: On the Days 3 and 4, mitoXANTRONE should be given 8 hours after the 5th and 7th high dose cytarabine infusions are completed.

See [Section 5.0 for Dose Modifications based on Toxicities.](#)

Patients who do not achieve a complete morphological remission after the end of Induction II will go off protocol therapy.

Intensification I will be administered to high risk DS AML patients with a morphologic CR (see [Section 10.2](#)) when ANC  $\geq$  1000/ $\mu$ L and platelets  $\geq$  100,000/ $\mu$ L. See [Section 4.1.6](#) for exceptions.

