##### Etoposide (ETOP): IV infusion over 90-120 minutes

Days: 1-5.

All patients : 5 mg/kg/day

Etoposide doses should immediately follow the 1st, 3rd, 5th, 7th, and 9th dose of cytarabine.

Infuse diluted solution (concentration  $\leq 0.4 \text{ mg/mL}$ ). The use of an in-line filter during the infusion is suggested. Slow rate of administration if hypotension occurs.

See [Section 5.1.2](#) on Allergy to Etoposide.

See [Section 5.0](#) for Dose Modifications based on Toxicities.

It is required that patients have an ANC  $\geq 1000/\mu\text{L}$  and a platelet count  $\geq 100,000/\mu\text{L}$  before proceeding with Intensification II. See [Section 4.1.6](#) for exceptions.

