### **Daunorubicin, Etoposide and Mitoxantrone**

Dosage adjustments should be made as indicated in the table below:

Direct Bilirubin	Daunorubicin	Etoposide	Mitoxantrone
≥ 2 and < 3 mg/dL	50% of the calculated dose	50% of the calculated dose	50% of the calculated dose
≥ 3 and < 5 mg/dL	25% of the calculated dose	25% of the calculated dose	25% of the calculated dose
≥ 5 mg/dL	Hold dose	Hold dose	Hold dose

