As of August 25, 2020, 32 of the 222 patients enrolled are HR patients who continued to Induction II and 5 patients have not been risk classified yet. Assuming 10% of enrolled patients will be HR, enrollment of up to 312 patients will be required to assure that there are 41 HR patients who continue to Induction II. Based on an accrual estimate of 60 patients per year, accrual of an additional 90 patients is expected to be completed in approximately 1.5 years.

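### Section 5.5.2 gives two different bilirubin thresholds for reducing daunorubicin, etoposide and mitoxantrone, so a child at 2 to < 3 mg/dL could receive full or half dose

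*Combined protocol and SAP*

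**What the plan says.** Section 5.5.2 (Hyperbilirubinemia) begins with a condition and an instruction: when conjugated (direct) bilirubin is above 3 mg/dL "and is not a result of the leukemia, modify the doses of daunorubicin, etoposide, and mitoxantrone as follows below". It then adds advice for any case in which direct bilirubin is raised "at the point in time that the next cycle is to begin, consider delaying the cycle for 1 week", to see whether the value falls.

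Under the sub-heading for the three drugs there is a second instruction, "Dosage adjustments should be made as indicated in the table below". It repeats neither the 3 mg/dL trigger nor the exception for leukemia. The table has three bands, the same for each drug:

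- 2 to < 3 mg/dL: 50% of the calculated dose
- 3 to < 5 mg/dL: 25%
- 5 mg/dL or more: hold

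Two other places bear on whether the case can arise. Section 3.2.4 says "There are no minimal organ function requirements for enrollment on this study" and refers significant organ dysfunction to Section 5.0. Section 4.2.2 requires the baseline studies before protocol therapy starts, and item d includes "bilirubin (unconjugated and conjugated), weekly while in the hospital".

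**The concern.** The lead-in and the table are meant to be one rule, but they start at different values. If the lead-in decides when the table is used, the 50% row can never apply, and dosing falls from full straight to 25%. If the table stands alone, reduction starts at 2 mg/dL and the leukemia exception is not stated.

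The difference is two-fold in the dose of cytotoxic drugs given to children under 4 years. Full dose in a child with impaired hepatic excretion risks excess toxicity. An unintended half dose under-treats a curable leukemia, including in the arm designed to intensify treatment. Two sites could treat the same child differently, and both could say they followed the protocol.

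**Working it through.** **1. Set the two rules side by side (bilirubin not due to leukemia).**

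| Direct bilirubin (mg/dL) | Lead-in as trigger | Table alone |
|---|---|---|
| 2 to < 3 | no modification (full dose implied) | 50% |
| exactly 3.0 | no modification, since 3.0 is not > 3 | 25% |
| > 3 to < 5 | use table: 25% | 25% |
| 5 or more | use table: hold | hold |

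No value is both above 3 and below 3, so the first row is empty under the lead-in. If the lead-in had been meant as 3 or more, the conflict at exactly 3.0 would disappear, but the first row would still be unreachable.

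**2. Look for text that settles it.** The treatment sections and delivery maps for Induction I, Induction II and Intensification I only point back to Section 5.0. The one-week delay is something to consider, is worded for the start of the next cycle, and sets no dose if bilirubin stays at 2 to < 3. It reduces exposure before Induction II and Intensification I, but it does not clearly cover Day 1 of Induction I.

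**3. Check that the case can arise.** No organ-function limit at entry keeps such a child out. Conjugated bilirubin is required before therapy. It is also among the Day 1 studies for Induction II (items a–h) and Intensification I (items a–f). The clinician has the value when choosing the dose.

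**4. Dose consequence at 2 to < 3 mg/dL, per cycle.**

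- Daunorubicin, Induction I (Section 4.2.3), Days 1–4. From 36 months: 20 × 4 = 80 mg/m², half = 40 mg/m². Under 36 months: 0.67 × 4 = 2.68 mg/kg, half = 1.34 mg/kg.
- Mitoxantrone, Induction II (Section 4.3.3), Days 3–6, "All patients: 0.4 mg/kg/day": 0.4 × 4 = 1.6 mg/kg, half = 0.8 mg/kg.
- Etoposide, Intensification I (Section 4.4.3), Days 1–5, "All patients : 5 mg/kg/day": 5 × 5 = 25 mg/kg, half = 12.5 mg/kg.

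**5. Arm B cumulative anthracycline, in daunorubicin equivalents.** First reproduce Table 1. Mitoxantrone is 12 × 4 = 48 mg/m² (Section 2.7), and at the 3:1 conversion 48 × 3 = 144. Then 80 + 144 = 224 mg/m², as Table 1 states. With halving:

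- Induction I only: 40 + 144 = 184
- Induction II only: 80 + 72 = 152
- both: 40 + 72 = 112

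Section 2.5 gives 272 mg/m² for the same arm. The 3:1 arithmetic supports 224, which is used here.

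**6. Patients still to be treated.** At the Amendment 6 count in Section 9.2, "32 of the 222 patients enrolled are HR patients who continued to Induction II". That leaves 312 − 222 = 90 further enrollments and 41 − 32 = 9 further high-risk patients. These are ceilings on how many a correction could reach, not estimates of how many have bilirubin in the band.

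**The case against.** The best counter-argument is that the lead-in does not contain the word *only* and nowhere prescribes full dose at 3 mg/dL or below. The table has its own heading and an unconditional instruction, so 50% is the only dose written down for 2 to < 3 mg/dL. Many clinicians would follow it as the more specific and more protective text. This is fair, and the full-dose reading is indeed an inference. But the lead-in says the modification follows below, and a condition that introduces a table is normally read as limiting it. The limiting reading is open to a site, and the protocol does not exclude it.

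Second, the frequency is unknown. The counts of 90 and 9 are simply all remaining accrual, the 112 mg/m² figure needs raised bilirubin at two separate cycles, and 3.0 mg/dL is a single value. All of that stands: the finding gives the size of the dose difference, not the number of children affected.

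Third, at Induction I much hyperbilirubinemia may be attributed to leukemia, and the lead-in exempts it at any threshold. That narrows the affected group. It also shows a second gap, because the table's own instruction carries no such exemption.

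Fourth, the documents do not reveal the intended threshold, and halving an anthracycline has a cost in disease control. This is correct, so the fix below leaves the committee room to confirm 3 mg/dL.

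**Conclusion.** The concern holds. Section 5.5.2 states two incompatible starting points for dose reduction in current text, and no other section resolves them. At 2 to < 3 mg/dL the two readings differ by a factor of two for all three drugs; at exactly 3.0 mg/dL the difference is full dose against 25%. Above 3 mg/dL, when leukemia is not the cause, they agree.

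This rests on reading the lead-in as the condition for using the table, and on the rise not being due to leukemia. The number of affected children cannot be derived from the documents. The point concerns individual dosing safety only; no effect on power, type I error or the primary analysis is claimed. It should still be corrected, because the plan leaves a cytotoxic dose in young children undetermined.

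**What to change.** Default: reword the lead-in so that the trigger is direct bilirubin of 2 mg/dL or higher, not caused by the leukemia, with the three drugs then adjusted by the table. Every row becomes reachable, and the rule matches the only dose the protocol tabulates for this band.

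Alternative, only if the study committee confirms that 3 mg/dL was intended: delete the first row and set the trigger at 3 mg/dL or higher, which also removes the conflict at exactly 3.0.

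In either case, state whether the leukemia exception applies to all rows or name the rows it covers, and send sites a clarification memo.

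The cost is one sentence or one table row plus the memo. Sample size, analysis and data collection do not change.

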### **Asparaginase**

Asparaginase has been associated with hepatic toxicity but dosing guidelines for hepatic toxicity are not available. Thus, asparaginase administration (*E.coli* or *Erwinia*) in the setting of hepatic toxicity is at the clinician's discretion.

### **Daunorubicin, Etoposide and Mitoxantrone**

Dosage adjustments should be made as indicated in the table below:

Direct Bilirubin	Daunorubicin	Etoposide	Mitoxantrone
≥ 2 and < 3 mg/dL	50% of the calculated dose	50% of the calculated dose	50% of the calculated dose
≥ 3 and < 5 mg/dL	25% of the calculated dose	25% of the calculated dose	25% of the calculated dose
≥ 5 mg/dL	Hold dose	Hold dose	Hold dose

## 5.6 Hyperglycemia

Do not modify the dose of asparaginase. Treat hyperglycemia as medically indicated.

## 5.7 Hyperlipidemia

Do not modify the dose of asparaginase.

## 5.8 Hypotension

If diastolic or systolic blood pressure (BP) falls 20 mmHg during infusion of etoposide, reduce infusion rate by 50%. Start a simultaneous infusion of NS 10 mL/kg if BP fails to recover or falls further. Stop infusion if BP does not recover, continue NS. If the patient has had any episode of hypotension, prehydrate with 0.9% NaCl at 10 mL/kg/hr for 2 hours prior to any subsequent infusion.

## 5.9 Ketoacidosis

Hold asparaginase until blood glucose can be regulated with insulin.

## 5.10 Neurologic Toxicity

The most common nervous system adverse event is an acute cerebellar syndrome that may manifest itself as ataxia, nystagmus, dysarthria, or dysmetria. However, seizures and encephalopathy have also occurred following therapy with high dose cytarabine.

Patients with ≥ Grade 3 CTCAE version 5.0 nervous system disorders from high dose cytarabine should not receive further high dose cytarabine. **Grade 3 or higher neurotoxicity from high-dose cytarabine (HR group, Arm B only) is a criterion for removal from protocol therapy.**

## 5.11 Pancreatitis

Discontinue asparaginase (*E.coli* or *Erwinia*) in the presence of hemorrhagic pancreatitis or severe pancreatitis (Grade 3-4). In the case of mild pancreatitis after Day 2 (< Grade 3 using CTCAE version 5.0 criteria), Day 9 asparaginase (*E.coli* or *Erwinia*) may be given only if symptoms and signs subside.

## 5.12 Renal Toxicity

### 5.12.1 Cytarabine

Patients with nephrotoxicity secondary to antibiotics, or antifungals, may have prolonged excretion of cytarabine leading to increased bone marrow and extramedullary toxicity. Patients with a serum creatinine > 2 mg/dL or > 2x normal

for age should be hydrated orally or intravenously. Following hydration, the patient must have a creatinine clearance  $\geq 60$  mL/min/1.73m^2 as measured preferably by a nuclear GFR scan, timed urine collection for creatinine clearance, or calculated by the Schwartz formula before proceeding with HD cytarabine therapy (doses of  $> 1$  g/m^2). If the CrCl is abnormal ( $< 60$  mL/min/1.73m^2) then high dose cytarabine should be reduced from twice daily to once daily dosing, at the same previously prescribed doses (e.g., 50% daily dose reduction). With this approach, previous research has prevented subsequent neurotoxicity in recipients of high dose cytarabine in the face of renal insufficiency.

#### 5.12.2 Etoposide

In patients with impaired renal function, the following **initial** dose modification of etoposide should be considered based on measured or calculated creatinine clearance: for CrCl  $> 60$  mL/min/1.73m^2 give full dose, for CrCl of 15-60 mL/min/1.73m^2 give 75% of the dose (25% dose reduction). **Subsequent doses** should be based on patient tolerance and clinical effect.

#### 5.13 **Thrombosis**

Discontinue asparaginase and treat with appropriate antithrombotic therapy, as indicated.

### 6.0 DRUG INFORMATION

Please see [Appendix IV](#) for drug interactions associated with the drugs used in this study.

See the consent document for toxicities. All other information is available on the COG website in the Commercial Agent Monographs ([https://www.cogmembers.org/\\_files/disc/pharmacy/CommercialAgentsMonographs.pdf](https://www.cogmembers.org/_files/disc/pharmacy/CommercialAgentsMonographs.pdf)) and is provided under Standard Sections for Protocols at: [https://cogmembers.org/site/pages/default.aspx?page=Prot\\_reference\\_materials](https://cogmembers.org/site/pages/default.aspx?page=Prot_reference_materials).

## 7.0 EVALUATIONS/MATERIAL AND DATA TO BE ACCESSIONED

Timing of protocol therapy administration, response assessment studies, and surgical interventions are based on schedules derived from the experimental design or on established standards of care. Minor unavoidable departures (up to 72 hours) from protocol directed therapy and/or disease evaluations (and up to 1 week for surgery) for valid clinical, patient and family logistical, or facility, procedure and/or anesthesia scheduling issues are acceptable (except where explicitly prohibited within the protocol).

### 7.1 End of Therapy & Follow-up

Observation	End of Therapy	1 month off therapy	Monthly for first 12 months from completion of therapy	Every 3 months for month 12 to 24 from completion of therapy	Every 6 months from month 24 until 5 years following completion of therapy	Annually for 10 years following completion of therapy	At relapse
Physical exam	■	■	■	■	■		■
Height, weight	■	■	■	■	■		■
CBC with diff/platelets	■	■	■	■	■		■
Creatinine, BUN	■	■					■
Electrolytes, Ca ++ , PO 4 , Mg ++	■	■					■
AST, ALT, Bilirubin unconjugated and conjugated	■	■					■
ECG	■					■	■
MUGA or ECHO	■					■	■
Unilateral BM Asp/Biopsy*							■
Bone marrow for banking							■

\* If unable to obtain a bone marrow aspirate

See COG Late Effects Guidelines for recommended post treatment follow-up:

<http://www.survivorshipguidelines.org/>

**Note:** Follow-up data are submitted per the Case Report Forms (CRFs) schedule.

## 7.2 Research Studies

Study	Specimen	Pre-treatment	End of Induction I	End of Induction II (High Risk Patients ONLY)
MRD	Bone marrow	X #	X	X
GATA-1 mutation analysis	Bone marrow	O	O	
Banking	Bone marrow	O	O	

X: Required

O: Optional requires patient consent.

#: If a bone marrow sample cannot be obtained, please send a blood sample (see [Section 14.1](#)).

For additional details on research studies, see [Section 14.0](#).

## 8.0 CRITERIA FOR REMOVAL FROM PROTOCOL THERAPY AND OFF STUDY CRITERIA

### 8.1 Criteria for Removal from Protocol Therapy

- a) PR, RD, or relapse following Induction II.
- b) Persistent CNS leukemia after 6 doses of IT Ara-C after Induction I.
- c) Grade 3 or greater neuropathy, myelitis and nervous system disorder, and other, including cerebellar toxicity from HD Ara-C (HR group, Arm B only).
- d) Refusal of further protocol therapy by patient/parent/guardian.
- e) Completion of planned therapy.
- f) Physician determines it is in patient's best interest.
- g) Development of a second malignancy.
- h) Repeat eligibility studies (if required) prior to the initiation of protocol therapy are outside the parameters required for eligibility (see [Section 3.2](#)).
- i) Failure to obtain a result for the MRD test at the end of Induction I.

Patients who are off protocol therapy are to be followed until they meet the criteria for Off Study (see below). Follow-up data will be required unless patient is taken off study.

### 8.2 Off Study Criteria

- a) Death.
- b) Lost to follow-up.
- c) Patient enrollment onto another COG study with tumor therapeutic intent (e.g., at recurrence).
- d) Withdrawal of consent for any further data submission.
- e) Tenth anniversary of the date the patient was enrolled on this study.
- f) For patients enrolled after the implementation of Amendment #4A: Patient is Standard Risk (MRD < 0.05% in the bone marrow) after Induction I.

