## 2.9

### **Interim Analysis of Patients Treated on the Standard Risk Arm**

According to the study analysis plan, an interim analysis of treatment outcomes for lack of efficacy on the Standard Risk (SR) arm (Arm A) was performed after 50% of the expected number of EFS events had been observed (after 8 of 16 events). Based on a model generated using data of SR patients in the historical control (predecessor study AAML0431) and the amount of follow-up available at the time of data cut off (30 June 2018), 2.4 EFS events were expected in SR patients compared to 8 EFS events observed. The projected 2-year EFS for SR patients on AAML1531 is significantly lower than on AAML0431 (85.6% compared to 93.5%, p 0.0002). As of October 5, 2018, 9 of 109 SR patients on AAML1531 have experienced a relapse at 136 to 327 days after study entry. Four of these relapses occurred on therapy (1 during Intensification I, 3 during Intensification II) and 5 during the first 6 months of follow up after completion of protocol therapy. Of the 9 relapsed SR patients, 8 have died.

These data show lack of sufficient efficacy of AAML1531 protocol therapy for SR patients. Based on this information, post-Induction I treatment on the SR Arm A of AAML1531 was permanently closed.

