#### 4.1.4 Standard Risk Patients

Standard risk patients are those with an MRD level of  $< 0.05\%$  at the end of Induction I. **Arm A for Standard Risk patients closed to accrual and treatment with amendment #4A.** Patients enrolled after amendment #4A who are Standard Risk after Induction I will be removed from study and will continue treatment off protocol per standard of care. No further data will be collected on these patients.

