## 9.0 STATISTICAL CONSIDERATIONS

### 9.1 Statistical Design

This study is a non-randomized study of children with DS and AML. The primary endpoint of interest will be the event-free survival (EFS) from the end of Induction I to failure to achieve remission at the end of Induction II, relapse, occurrence of a second malignancy or death.

Other outcome measures will include average total number of days per patient spent on protocol therapy, early death rates, overall survival from on study, treatment related mortality, relapse risk, percentage of patients experiencing Grade 3 or higher toxicity, time to count recovery, duration of hospitalization, and infection rates.

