## 9.3 Statistical Analysis Methods

### 9.3.1 Analysis Plan

The Kaplan-Meier method will be used to estimate 2-year EFS from the end of Induction I along with 95% log-minus-log transformed confidence limits separately for HR and SR patients at end of Induction I. To compare the Kaplan Meier estimate of 2-year EFS (KM2) with fixed values, we will use the test statistic  $\frac{\ln(-\ln(\text{KM2})) - \ln(-\ln(0.935))}{\text{Estimated SD} [\ln(-\ln(\text{KM2}))]}$  for SR and  $\frac{\ln(-\ln(\text{KM2})) - \ln(-\ln(0.76))}{\text{Estimated SD} [\ln(-\ln(\text{KM2}))]}$  for HR patients and compare these with a standard normal distribution.

\* Updated with Amendment #4A

AAML1531 was temporarily closed to accrual on October 1, 2018, due to results of an interim analysis identifying a significantly lower EFS for SR patients than that expected based on comparative data from AAML0431. Post-Induction I treatment on the SR Arm A was permanently closed on October 18, 2018. All patients enrolled prior to amendment #4A who were assigned to the SR arm were to be taken off protocol therapy but may stay on study. These SR patients enrolled prior to amendment #4A who are taken off protocol therapy due to the closure of treatment on the SR arm will be censored in future EFS analysis at the time they were taken off protocol therapy. Patients enrolled after amendment #4A who are assigned to the SR arm will be removed from study and continue treatment off protocol per standard of care. No further data will be collected on these patients.

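### Required follow-up ends when a relapsed child joins another COG treatment study, and the plan does not say how overall survival is then completed

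*Combined protocol and SAP*

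**What the plan says.** Section 9.1 lists "overall survival from on study" among the other outcome measures. Section 8.1 makes relapse a reason to stop protocol therapy, but not by itself a reason to stop follow-up: "Patients who are off protocol therapy are to be followed until they meet the criteria for Off Study (see below"). It then limits the duty to report: "Follow-up data will be required unless patient is taken off study". Section 8.2(c) gives as one off-study criterion "Patient enrollment onto another COG study with tumor therapeutic intent (e.g., at recurrence").

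The plan states no estimator and no censoring rule for OS. The only explicit censoring rule, in section 9.3.1, concerns a different endpoint and group. SR children taken off therapy when their arm closed "will be censored in future EFS analysis at the time they were taken off protocol therapy".

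Two passages describe the outlook after failure. Section 2.6 cites a 3-year OS of 25.9% among 29 children with relapsed or refractory disease. Section 2.9 reports on this trial's SR arm as of October 2018: "Of the 9 relapsed SR patients, 8 have died".

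**The concern.** A Kaplan-Meier curve treats a censored child as having the same outlook as those still under observation. A child who leaves under 8.2(c) at recurrence has a far worse outlook than a child in remission. If the reporting rule is followed literally and nothing replaces the lost data, that child is counted as alive up to the exit and then leaves the risk set, and a later death is never counted. The error runs one way: OS looks better than it is.

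The HR arm is where this could matter. In AAML0431, 2-year EFS and 2-year OS were both 76% in MRD-positive children (section 2.10.2.2). In such a group, OS depends largely on deaths that follow failure, which are the deaths this clause can hide. A reader who sets the new HR OS beside the earlier 76% would then see a comparison tilted towards the intensified regimen.

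**Working it through.** The documents give no OS target, power or event count, so there is no stated figure to reproduce. The check asks how far Kaplan-Meier OS moves if a share q of failures is censored soon after failure.

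**Inputs from the documents**
- HR event model, section 9.3.2: S(t) = 0.75 + 0.25·exp(−0.0037t), t in days. At 730 days, S = 0.75 + 0.25 × 0.0671 = 0.767.
- Slower mortality after failure, section 2.6: 25.9% alive at 3 years.
- Faster mortality after failure, section 2.9: 8 of 9 dead.

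**Assumptions (not in the documents)**
- All failures are relapses.
- Time from failure to death is exponential.
- The 8-of-9 figure is reached in 1 year.
- Children who leave do so 0, 30 or 60 days after failure.
- q is free. Time runs from the model's origin.

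**Death rate after failure**
- Slower: λ = −ln(0.259)/1095.75 = 0.001233 per day.
- Faster: λ = −ln(1/9)/365.25 = 0.006016 per day.

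**OS with complete follow-up.** The proportion alive after failure is R(t) = [0.25 × 0.0037/(0.0037 − λ)] × [exp(−λt) − exp(−0.0037t)], and OS(t) = S(t) + R(t). At 730 days:
- Slower: R = 0.375 × (0.4066 − 0.0671) = 0.127, so OS = 89.4%.
- Faster: R = −0.3994 × (0.0124 − 0.0671) = 0.022, so OS = 78.9%.

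**OS with informative censoring.** If a share q leaves at failure, Kaplan-Meier converges to exp{−∫ λ(1−q)R/[S + (1−q)R] dt}. With a delay before leaving, those who failed within that delay stay in the risk set. Numerical integration to 730 days gives (differences taken before rounding):

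| Mortality after failure | Leaves after | Complete OS | q = 25% | q = 50% |
|---|---|---|---|---|
| Slower | 0 days | 89.4% | 91.7% (+2.3) | 94.2% (+4.8) |
| Slower | 30 days | 89.4% | 91.5% (+2.1) | 93.8% (+4.4) |
| Slower | 60 days | 89.4% | 91.3% (+1.9) | 93.4% (+4.0) |
| Faster | 0 days | 78.9% | 83.5% (+4.6) | 88.5% (+9.6) |
| Faster | 30 days | 78.9% | 82.6% (+3.8) | 86.7% (+7.8) |
| Faster | 60 days | 78.9% | 82.0% (+3.1) | 85.2% (+6.4) |

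A variant uses 8/9 of failures fatal, a mean of 150 days to death and leaving at failure. It gives +4.3 and +8.9 points when EFS is 76%, and +2.3 and +4.7 points when EFS is 88%. At q = 0 the bias is zero in every case.

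**What the SR data say about q.** Eight of nine relapsed children were known to have died, so at most 1 of 9 (11%) was lost before death. At q = 1/9 and a 30-day delay, the HR model gives +0.9 (slower) to +1.6 (faster) points.

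**Scale.** With 41 HR patients, failures number about 41 × 0.24 = 9.8 at 76% EFS and 41 × 0.12 = 4.9 at 88%. A 25% share is therefore one to three children. The standard error of a 76% estimate in 41 patients is √(0.76 × 0.24/41) = 6.7 points.

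**The case against.** The strongest reply is that no bias has been shown. The plan gives no OS censoring rule, so censoring at re-enrolment is an inference. Section 3.1.1 says that one COG patient ID serves all later dealings with the group, so vital status could be linked. The deaths recorded in section 2.9 show that most deaths after relapse were captured in the SR arm. The larger figures above need fast mortality, prompt leaving and a high share. They also treat every failure as able to re-enrol, although a death as first event cannot be hidden by this clause. OS is an unpowered secondary outcome, and the sampling error in 41 patients is as large as most of the illustrated biases.

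Most of this stands and limits the size of the point. It does not remove it. Sections 8.1 and 8.2(c) together state a rule that releases sites from reporting, and the possibility of linkage is not a plan to use it. Capture in the SR arm up to October 2018 does not show what will happen in the HR arm.

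A reader might infer three stronger things that the documents do not support:

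- **That OS is the main safeguard against trading relapse for death.** Section 9.3.2 has a toxic-death rule, and section 9.1 lists treatment-related mortality and early death separately.
- **That 8.2(f) distorts a whole-cohort OS.** After Amendment 4A, SR children leave at the end of Induction I and "No further data will be collected on these patients". However, no pooled OS is planned. The aims are set by risk group, and section 9.3.1 estimates EFS separately for each. Carrying AAML0431's 96% OS over to the 109 SR patients would also conflict with at least 8 deaths among them: 101/109 = 92.7% at best.
- **That OS should start at the end of Induction I.** Starting at study entry is legitimate and keeps deaths during Induction I.

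**Conclusion.** The concern holds in conditional form. As written, the plan lets required follow-up stop at a moment tied to relapse while OS remains a reported outcome, and it does not say how vital status is then obtained. If any relapsed child leaves under 8.2(c) and is censored there, Kaplan-Meier OS is biased upward. The plan does not support saying that OS will be overstated, because neither the share leaving nor the handling of those children is given.

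For HR 2-year OS, the illustrated overstatement is about 2 to 4 points at a 25% share and about 4 to 9 points at 50%. The most extreme combination (faster mortality, leaving at once) reaches 4.6 and 9.6. With 88% EFS, the 150-day variant gives roughly half its values at 76%. These sizes rest on assumed mortality and timing after failure, and the SR experience suggests that the true effect may be small.

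The primary EFS comparison is not affected by children who leave at recurrence, because the EFS definition already counts "relapse, occurrence of a second malignancy or death". This is a cheap improvement to a secondary outcome, not a flaw in the main analysis.

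**What to change.** - **Section 8.2(c):** end treatment and toxicity data collection on enrolment in another COG therapeutic study, but keep vital status and date of last contact, taken from the later study through the COG patient ID.
- **Sections 9.1 and 9.3:** state that OS is not censored at that enrolment, and give the OS estimator and censoring date.
- **Report:** give the number of children in each risk group who left under 8.2(c) and how many have linked vital status.

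If linkage is already routine, one sentence saying so settles the point. The cost is amendment wording and modest data-linkage work. Treatment, sample size and the EFS analysis do not change.
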